6.7 Intervention After the End of the Study

After completing dosing with study drugs at Week 20 and the Follow-up Visit at Week 24, the participants will have completed the study. AZD5718 will not be provided for post-study use. Both the study drugs (AZD5718 and dapagliflozin) will be withdrawn after Week 20 and participants should be returned to their previously prescribed treatment regimen, at the discretion of the Investigator.

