4.5.1 Analysis Sets

Analysis sets consist of two components: (1) analysis population (See Section 4.5), which specifies the participants included in an analysis; (2) data period, defining the time period during which data will be included in the analysis.

Analysis Set	Analysis Population	Data Period
Full Analysis Set	Full Analysis Population	Day 1 to the end of the follow-up period
Per-Protocol Set	Per-Protocol Population	Day 1 to the end of the follow-up period
Safety Analysis Set	Safety Analysis Population	Day 1 to the end of the follow-up period
Monotherapy Safety Analysis Set	Safety Analysis Population	Day 1 to the end of the first treatment period
Extended Safety Analysis Set	Extended Safety Analysis Population	Day 1 to the end of the follow-up period with flag to subset Week 12 to the end of the follow-up period

The Extended Safety Analysis Set includes participants who entered the second treatment period. The Week 12 flag is added to the Extended Safety Analysis Set to allow subsetting of participant data to be from Week 12 to end of study.

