4.10 Safety Evaluation

All safety summaries and analyses will be based upon the Safety analysis set as defined in Section 4.5, unless otherwise specified. Safety summaries will be presented by treatment group and with a pooled AZD5718 group, where appropriate.

Change from baseline will be calculated as the differences between the post-dose value at each time point and the value prior to administration of the study medication.

Individual safety and tolerability data will be provided in data listings and summarised as appropriate by treatment and overall. Continuous variables (laboratory parameters, ECG, and blood pressure) will be summarised using descriptive statistics (n, mean, SD, minimum, median, and maximum) as appropriate by scheduled assessment time point. Where applicable, data will be summarised for the observed value, and for the corresponding change from baseline/screening. Categorical variables will be summarised in frequency tables (counts and percentage) as appropriate by scheduled assessment time point too.

Outputs presented on the Extended Safety Analysis Set will include the Week 12 flag to subset for data in the second treatment period. These outputs may be repeated without the Week 12 flag if deemed appropriate by the study team, thereby including all data for participants who continued into the second treatment period only.

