4.10.2 Adverse Events

Adverse events will be coded using MedDRA version 23.0 or later.

An AE (classified by preferred term) started during the treatment period will be considered a treatment-emergent adverse event if it was not present prior to the first dose of randomised treatment. An AE that starts more than 7 days after the last dose of study medication will not be counted as a treatment-emergent AE. AEs which worsen after the start of treatment will not be included as a treatment-emergent AE but will be recorded.

Adverse events (and also separately SAEs) will be summarised by study treatment group in incidence summaries by MedDRA SOC and PT. Adverse events will be assigned to the period where they start and will be summarised for the Safety Analysis Set, with selected outputs summarized for the Monotherapy Safety Analysis Set and Extended Safety Analysis Set with Week 12 flag. Serious adverse event collection will begin after the participant signs the informed consent document, and all AE collection will begin after the participant has received the first dose of the study drug. The SAE/AE collection will last until the end of the participant’s follow-up period.

All AEs will be listed and assigned to on/off treatment period as:

- Prior treatment: The SAE occurred before the first administration of study drug. Only applicable for SAEs.
- On treatment: The AE occurred on or after the first administration until 7 days after last dose of AZD5718 and/or dapagliflozin.
- Off treatment: The AE occurred more than 7 days after the last dose of study drug.

The number, percentage and percentage per participant exposure year (PEY) of participants reporting treatment-emergent AEs in each treatment group will be tabulated by SOC and PT; by SOC; by SOC, PT, and relationship to study medication as assessed by the Investigator. If more than one event occurs with the same preferred term for the same participant, the participant will be counted only once for that preferred term using the most severe and most related occurrence for the summarisation by severity and by relationship to the study medication.

The event rate per 100 PEY is defined as:

$$\left(\frac{\text{number of subjects with AE}}{\text{sum of days at risk for AE in treatment period} + 7 \text{ days}} \right) \times 365.25 \times 100$$

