The denominator is calculated per participant then summed. The distribution of treatment-emergent AEs by severity and relationship to study medication will be summarized by treatment group.

A summary of AEs in any category will be presented by treatment. The incidence of common ($\geq 5\%$ of participants in any treatment group) treatment-emergent AEs, common treatment-emergent serious AEs, and AEs leading to discontinuation of study medication will be summarized by SOC, PT and treatment group, sorted in decreasing overall (across treatments) frequency. Treatment-emergent AEs with outcome of deaths will also be presented. In addition, all fatal SAEs (ie, events that caused death) will be summarized. For each participant and each AE, the worst intensity recorded will be attributed and used in the by-intensity summaries. Similarly, the worst causality will be attributed and used in the by-causality summaries. Multiple occurrences of a treatment-emergent AE in the same participant will only be counted once overall. Non-serious treatment-emergent AEs occurring in more than 5% of participants will be presented by treatment.

The number and percentage of participants reporting AEs by treatment group, SOC and PT will also be presented for the Monotherapy Safety Analysis Set and the Extended Safety Analysis Set with Week 12 flag.

Listings will be presented of participants with SAEs, AEs leading to discontinuation, and participants who died. A listing will be presented of participants with AEs, detailing whether these are SAEs, AEs leading to discontinuation, or result in death. Listings will include on- and off-treatment categorization.

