4.10.4 Clinical Laboratory Evaluation

The following summaries will be provided:

- A summary of the observed absolute values and change from baseline in each haematology and clinical chemistry laboratory parameter by treatment group and time point.
- A summary of baseline versus maximum observation on treatment in each laboratory parameter by treatment group (shift table)
- A summary of baseline versus minimum observation on treatment in each laboratory parameter by treatment group (shift table)
- A summary of key participant information for participants reporting changes outside reference ranges in each laboratory parameter
- A summary of the number and percentage of participants reporting changes outside reference ranges in each laboratory parameter
- A plot of alanine aminotransferase (ALT) versus total bilirubin, expressed as multiples of upper limit of normal (ULN)
- A plot of aspartate aminotransferase (AST) versus total bilirubin, expressed as multiples of ULN
- A plot of liver biochemistry over time, for participants with potential Drug Induced Liver Injury (ie, $ALT/AST \geq 3 \times ULN$ and total bilirubin (BILI) $\geq 2 \times ULN$, and in which the elevation in transaminases precede or coincide with (that is, on the same day as) the elevation in BILI or $ALT/AST \geq 5 \times ULN$)
- A summary of the number and percentage of participants reporting maximum on-treatment ALT and AST by maximum total bilirubin for assessing Hy's Law criteria
- A summary of individual participant data for participants with Potential Hy's Law ie, participants with combined ALT or AST, and bilirubin elevations
- A summary of treatment-emergent laboratory changes will be presented for the Safety Analysis Set, the Monotherapy Safety Analysis Set (Treatment Period 1) and the Extended Safety Analysis Set with Week 12 flag (Treatment Period 2).

Treatment-emergent laboratory and vitals change (TELVC) limits of interest for this study are provided in [Appendix C](#) for the laboratory parameters, and in [Table 5](#) for vital signs.

By-participant listings of all laboratory data will be provided including participant identifier, treatment, age, sex, race, visit, category, laboratory test name, result, and standard units. Laboratory reference ranges will also be listed and out of range values will be flagged.

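### The Week 12 safety subset is presented as Treatment Period 2 but runs to the end of follow-up, so about three weeks of off-treatment data enter its SAE and laboratory tables

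*SAP*

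**What the plan says.** The SAP describes the Week 12-flagged subset in two ways.

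- **By data period.** The table in SAP 4.5.1 gives "Day 1 to the end of the follow-up period with flag to subset Week 12 to the end of the follow-up period". The sentence below that table says the flag is there "to allow subsetting of participant data to be from Week 12 to end of study".
- **By purpose.** SAP 4.10 says: "Outputs presented on the Extended Safety Analysis Set will include the Week 12 flag to subset for data in the second treatment period". The laboratory list in SAP 4.10.4 attaches the period name to it: "the Extended Safety Analysis Set with Week 12 flag (Treatment Period 2".

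Other sections fix where Treatment Period 2 ends. Protocol 9.4.1 lists follow-up as a separate 4-week period. Protocol 6.7 states: "Both the study drugs (AZD5718 and dapagliflozin) will be withdrawn after Week 20". The interim analysis sets in SAP Appendix B equate the end of Treatment Period 2 with Week 20.

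SAP 4.10.2 assigns each AE to the period in which it starts and sets the limit: "Off treatment: The AE occurred more than 7 days after the last dose of study drug". The same 7-day limit defines a treatment-emergent AE.

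Three kinds of table use the flagged subset:

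- an AE table (SAP 4.10.2): "The number and percentage of participants reporting AEs by treatment group, SOC and PT will also be presented for the Monotherapy Safety Analysis Set", and likewise for the flagged Extended set;
- tables of treatment-emergent AEs leading to death and of SAEs (SAP 4.10.3);
- the summary of treatment-emergent laboratory changes (SAP 4.10.4).

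The Monotherapy set, used for Period 1, stops at the end of the first treatment period.

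**The concern.** A programmer who follows SAP 4.5.1 includes every record from Week 12 to the Week 24 visit. A reader who follows SAP 4.10 and 4.10.4 takes the resulting table as data on AZD5718 or placebo plus dapagliflozin. These differ by the follow-up period, when both drugs have been withdrawn.

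The synopsis of the protocol says AEs in Treatment Periods 1 and 2 will be analysed separately, then overall. If follow-up is folded into the second of these, an SAE that starts four weeks after the last dose, or a raised creatinine at Visit 10, is reported under Treatment Period 2. Adding off-drug time can only raise the percentage of participants with an event. If drug effects fade after stopping, it also pulls the arms closer together in the tables meant to show the safety of the combination.

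**Working it through.** **Inputs.** Week 12 visit, Day 85; Week 20 visit, Day 141 (window 138 to 144); follow-up visit, Day 169 (window 164 to 174). These come from the schedules of activities and SAP 4.2, Table 2. The on-treatment limit is last dose + 7 days (SAP 4.10.2). The last dose is taken to fall on the Week 20 visit day, when the schedule has drug taken at the centre.

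**The plan's own figure.** Follow-up length = 169 − 141 = 28 days = 4 weeks, as protocol 9.4.1 states.

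**Length of the off-treatment tail**, follow-up day − (last-dose day + 7):

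- Nominal: 169 − (141 + 7) = 169 − 148 = 21 days.
- Shortest within the windows: 164 − (144 + 7) = 13 days.
- Longest within the windows: 174 − (138 + 7) = 29 days.
- A participant who stops both drugs on Day 113 but stays in the study, as protocol 7.1 expects: 169 − (113 + 7) = 49 days.

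**Share of the subset.** 169 − 85 = 84 days, of which 148 − 85 = 63 are within the limit. The share outside is 21/84 = 25% (21/85 = 24.7% if both end days are counted).

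**Which flagged tables are exposed.**

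| Flagged table | Time limit stated | Tail admitted? |
|---|---|---|
| Treatment-emergent AEs leading to death (4.10.3) | 7-day rule, through the definition | No |
| SAEs (4.10.3) | None | Yes |
| AEs by SOC and PT (4.10.2) | None; treatment-emergent is not stated | Yes, if read literally |
| Treatment-emergent laboratory changes (4.10.4) | None; Appendix C gives only limits of change | Yes, including Visit 10 |

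The shift tables in SAP 4.10.4 do restrict themselves to on-treatment values. The schedule has safety laboratory samples at Visit 10, nominally 28 days after the last dose.

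**Illustrations.** The incidences, hazard ratio and per-visit probabilities below are assumptions; the documents give none of them.

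- *Constant hazard:* p63 = 1 − (1 − p84)^(63/84). An incidence of 20% over 84 days corresponds to 15.4% over 63 days; 40% corresponds to 31.8%.
- *Hazard ratio 1.5 on drug and 1.0 after the limit, placebo 20% over 84 days:* the placebo cumulative hazard is −ln(0.8) = 0.2231, of which 0.1674 falls in the first 63 days and 0.0558 in the last 21. Over 63 days the risk ratio is (1 − e^(−0.2510))/0.1541 = 1.44. Over 84 days it is (1 − e^(−0.3068))/0.20 = 1.32.
- *Laboratory limits, independent visits with equal probability q:* the share of flagged participants flagged at Visit 10 alone is q(1 − q)^(k−1)/[1 − (1 − q)^k] for k samples. For q from 1% to 5%, this is 33% to 32% with k = 3 (Visits 8, 9, 10) and 25% to 23% with k = 4 (adding Visit 7, since the flag starts at Week 12). It is lower if abnormalities persist across visits.

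**Comparison with Period 1.** The Monotherapy window runs from Day 1 to Day 85, also 84 days. Under a constant hazard, the two tables as now defined would show the same percentage.

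**The case against.** The best defence is that SAP 4.5.1 states the window twice, so it is deliberate, and that keeping late SAEs in view is sound safety practice when collection continues through follow-up. Only Period 2 is followed by an off-drug interval, and those data must be placed somewhere. This explains the window but not the label: SAP 4.10 and 4.10.4 still call the contents the second treatment period.

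The AE table may also be meant as a repeat of the treatment-emergent table on the period sets. SAP 4.10.2 speaks of selected outputs on those sets, and uses the bare term AEs loosely elsewhere. That reading is plausible, so for the AE table the finding is an ambiguity. It does not cover the SAE table: SAP 4.10.3 restricts deaths to treatment-emergent events and leaves SAEs unrestricted in the same sentence.

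Some separation exists already. AE listings carry an on- or off-treatment category, the exposure-adjusted rate counts days at risk to 7 days after treatment, and by-visit summaries show Follow-up as its own analysis visit. These help a careful reader but do not alter the flagged tables.

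Two stronger inferences are tempting and fail. A reader might infer that the longer window makes Period 2 look worse than Period 1. The two windows are equal at about 84 days, so counting time alone does not do that. A reader might also take the flagged AE table as the only period-specific safety view. It is not: there are flagged death, SAE and laboratory tables, and visit summaries at Weeks 16 and 20.

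**Conclusion.** The contradiction stands. SAP 4.5.1 defines the flagged subset to the end of follow-up; SAP 4.10 and 4.10.4 present it as Treatment Period 2; Appendix B ends that period at Week 20. For a nominal completer, 21 of 84 days and the Visit 10 sample fall outside the on-treatment limit of SAP 4.10.2. That limit is written for AEs. The SAP gives no time window for treatment-emergent laboratory changes, so the data period governs and admits Visit 10.

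The exposed outputs are the SAE table, the laboratory summary and, on a literal reading, the AE table. The death table is protected. The primary efficacy result and the full-study treatment-emergent AE tables are unaffected.

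The 21 days describe a nominal completer. The study ended early, with 340 of 613 randomised participants completing treatment (SAP 4.14). Early termination visits may shorten the tail for some, and stopping drug mid-period lengthens it for others. Dilution of the contrast requires that drug effects fade after stopping. The incidence, risk-ratio and laboratory figures show possible size only; the contradiction does not depend on them.

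**What to change.** 1. In SAP 4.5.1, end the flagged subset used for the Period 2 AE, SAE and laboratory tables at the earlier of last dose of study drug + 7 days and end of study. Say in SAP 4.10.4 that this limit applies to the treatment-emergent laboratory summary.
2. Show later events and Visit 10 values in a separate follow-up column, so that nothing is lost.
3. State in SAP 4.10.2 whether the flagged AE table counts all AEs or only treatment-emergent ones.
4. The capped Period 2 window is about 63 days against about 84 for Period 1, so raw percentages would favour Period 2 through length alone. Compare periods with the exposure-adjusted rate already defined in SAP 4.10.2, using each period's own days at risk.

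The cost is a few lines of SAP text, one programming condition and an extra column. No new data are needed.

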- ^l Phone call will occur after results from Screening Visit 1 are available and the participant is confirmed eligible in order to remind the participants to collect the first morning void urine samples and schedule the Screening Visit 2. If scheduled Visit 3 (Week 1) or Visit 7 (Week 12) will need to be delayed due to the need to repeat ABPM recording there is no need to repeat collection of the 3 urine samples.
- ^m Participants to collect first morning void urine samples on 3 consecutive days (ideally day of visit and each of the preceding 2 days [refrigerated overnight] which are returned on the day of visit). This collection may be repeated once during the course of screening.
- ⁿ Participants will be provided an ABPM cuff at Screening Visit 2 and Visit 6 (Week 8) and instructed to perform ABPM 24-hours before their next visit ie, Visit 3 (Week 1) and Visit 7 (Week 12), respectively. Site will be asked to call the participant the day prior to next visit as a reminder to complete assessments. The participant may also visit the site for APBM cuff placement 1 day before their next visit of scheduled assessment (ie, Visit 3 [Week 1] and Visit 7 [Week 12] respectively).
- ^o Sites should ensure that the validity criterion described in Section 8.2.5 is met prior to completing any other assessments at the visit. If the validity criterion is not met, the associated study visit may be rescheduled to allow for a repeat ABPM recording only if the rescheduled visit can be completed within the specified tolerance period for study visits:
- Visit 3: up to 72 hours following the originally scheduled visit for Visit 3 but no more than 32 days from Screening Visit 1
 - Visit 7: \pm 72 hours from Day 85
- If a repeat ABPM session is not possible, the study visit should proceed as indicated. In addition, the visit should also continue if the ABPM session does not meet the validity criterion after the repeat session.

^p Study drug refers to AZD5718/placebo during Treatment Period 1 and AZD5718/placebo + dapagliflozin during Treatment Period 2.

^q Site should follow-up directly with the participant via phone to remind the participant.

^r Participants to return all study drug dispensed at previous visits and only use the newly dispensed study drug. Participants should be reminded not to take study drug on the days of a study visit until instructed by the study site.

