4 STUDY DESIGN

4.1 Overall Design

This is a Phase 2b, randomised, double-blind, placebo-controlled, multi-centre, dose-ranging study to evaluate the efficacy, safety and PK of AZD5718 in participants with proteinuric CKD. Furthermore, the additive effect of the SGLT2i dapagliflozin taken together with AZD5718 on albuminuria will be assessed in an 8-week extension period where participants will be treated with AZD5718/placebo and dapagliflozin.

The study will be conducted in approximately 118 study centres across 12 countries.

Approximately 632 participants comprising of 67% DKD and 33% non-DKD participants will be randomised 1:1:1:1 to receive once daily oral doses of [REDACTED] mg AZD5718, [REDACTED] mg AZD5718, [REDACTED] mg AZD5718, or placebo, for the first 12 weeks with an add-on therapy of 8 weeks of 10 mg dapagliflozin for all participants, to have 158 participants per group. The plan is to have approximately 568 evaluable participants (142 per group) completing the study.

The study will include 4 periods:

- Screening Period of up to 4 weeks.
- Treatment Period 1 of 12 weeks where the participants will receive a once daily oral dose of the assigned dose of study drug to be taken with approximately 200 mL water in the morning with no restrictions on food intake.
- Treatment Period 2 of 8 weeks where the participants will receive a treatment of once daily oral dose of dapagliflozin 10 mg in addition to the assigned dose of study drug. Only participants still taking their assigned treatment from Treatment Period 1 will progress to Treatment Period 2. Any participant with urine albumin to creatinine ratio (ACR) < 30 mg/g at Week 12 will be excluded from Treatment Period 2. The eligibility check to enter Treatment Period 2 will be done at Visit 7 (Week 12) using the last available urine ACR result, calculated as the geometric mean of the replicated measurements using 3 sequential first morning urine voids.
- Follow-up Period of up to 4 weeks.

The study will include a total of 10 visits which includes 2 visits during the Screening Period, 5 visits during the Treatment Period 1, 2 visits during the Treatment Period 2, and 1 visit during the Follow-up Period.

The expected total study duration, including the Screening Period, for each participant will be at least 28 weeks.

The SoA to be conducted during the study is presented in [Table 1](#) and a schematic

representation of the study is presented in [Figure 1](#).

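### The Period 2 safety subset starts at Week 12, not at the first dapagliflozin dose, so Visit 7 laboratory changes that precede dapagliflozin can be tabulated as Period 2, and in both periods

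*SAP*

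**What the plan says.** The analysis-set table in SAP 4.5.1 gives the Monotherapy Safety Analysis Set the data period "Day 1 to the end of the first treatment period". The Extended Safety Analysis Set, made up of participants who went on to dapagliflozin, carries a "flag to subset Week 12 to the end of the follow-up period". The text below the table says that the flag is there "to allow subsetting of participant data to be from Week 12 to end of study". None of these entries names a dose, a study day or an analysis visit.

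SAP 4.10 gives the purpose: outputs on the Extended set "will include the Week 12 flag to subset for data in the second treatment period". The last summary listed in SAP 4.10.4 shows treatment-emergent laboratory changes on the Safety set, on the Monotherapy set (labelled Treatment Period 1) and on "the Extended Safety Analysis Set with Week 12 flag (Treatment Period 2").

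Protocol 4.1 allots "5 visits during the Treatment Period 1, 2 visits during the Treatment Period 2". A footnote to the protocol's schedule of activities (Section 1.3) adds: "Participants should be reminded not to take study drug on the days of a study visit until instructed by the study site".

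**The concern.** The flagged subset is meant to describe safety on AZD5718 or placebo together with dapagliflozin. If it opens at the Week 12 visit, its first laboratory sample was taken on AZD5718 or placebo without study dapagliflozin. A creatinine rise or a potassium value beyond the SAP Appendix C limits at that visit would then be shown as a Period 2 finding. Because the Monotherapy set runs to the close of Period 1, and the protocol places Visit 7 in Period 1, the same value can also appear in the Period 1 summary.

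What is at stake is the attribution of laboratory abnormalities to one treatment phase or the other. Creatinine matters most, since renal function with and without dapagliflozin is itself a secondary objective.

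**Working it through.** The plan gives no figure to reproduce. The check sets the boundaries against the visit schedule and then illustrates the size.

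**1. Where Visit 7 sits.** Protocol 4.1 counts 2 screening + 5 Period 1 + 2 Period 2 + 1 follow-up = 10 visits. Period 1 is therefore Visits 3-7 and Period 2 is Visits 8-9. Visit 7 (Day 85 ± 3) closes Period 1.

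**2. When dapagliflozin starts.** Eligibility for Period 2 is checked at Visit 7, so dapagliflozin cannot start earlier. Dosing on a visit day waits for the site's instruction. Safety laboratory samples are fasting and taken in the morning. That they precede the dose is an inference: the laboratory row of the schedule does not carry the footnote requiring collection before study drug. Some DKD participants already take their own SGLT2 inhibitor in Period 1 (Protocol 6.5.2), so the accurate phrase is without study dapagliflozin.

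**3. What the flag captures under each possible derivation.**
- *By analysis visit:* the Week 12 window in SAP Table 2 is D72-D88. D72-D84 is 84 − 72 + 1 = 13 days before the D85 target. Scheduled Visit 7 samples enter Period 2, and so could unscheduled ones from those 13 days.
- *By Visit 7 date:* same-day samples taken before the dose enter Period 2.
- *By fixed Day 85:* Visit 7 may fall on D82-D88. Early attenders lose dapagliflozin days from the subset. Late attenders contribute days without it.
- *By first dapagliflozin dose:* nothing taken before the dose enters. The SAP does not state this rule.

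**4. Which values are affected.** SAP Appendix C sets treatment-emergent limits for creatinine, sodium, potassium and creatine kinase. The general baseline in SAP 4.2 is the last value before the first dose of study medication, and no separate Period 2 baseline is given. An abnormality that persists from Visit 7 to Week 16 therefore counts in Period 2 wherever the boundary lies.

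**5. Size, by assumption.** Let q be the chance of a treatment-emergent change at one draw, equal and independent across draws. The documents give no such rate, so q = 1-5% is assumed. The chance of at least one change in k draws is 1 − (1 − q)^k.

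| Draws counted | q = 1% | q = 5% |
|---|---|---|
| Weeks 16, 20 (k = 2) | 1.99% | 9.75% |
| Weeks 12, 16, 20 (k = 3) | 2.97% | 14.26% |
| Ratio, 3 v 2 | 1.49 | 1.46 |
| Weeks 16, 20, Follow-up (k = 3) | 2.97% | 14.26% |
| Weeks 12, 16, 20, Follow-up (k = 4) | 3.94% | 18.55% |
| Ratio, 4 v 3 | 1.33 | 1.30 |

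The flagged data period runs to the end of follow-up, so 4 v 3 matches the text better: a relative overstatement of 30-33%. Without the Follow-up draw it is 46-49%. If every Visit 7 abnormality recurs at a later counted draw, it is 0%.

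**The case against.** The strongest reply is that SAP 4.10 states the intent, which is to select data from the second treatment period, and a sensible programmer would cut at the first dapagliflozin dose. The intent is clear, but the operative definition in 4.5.1 says Week 12. The purpose sentence shows that the definition misses its aim; it does not replace the definition.

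Other parts of the reply stand, and they limit the point:
- A reader might infer that Visit 7 vital signs and ECGs are also tabulated as Period 2 or counted twice. The SAP does not support this. By default "All safety summaries and analyses will be based upon the Safety analysis set", and 4.10.5 specifies no split by period for either. The ECG summary presents readings both before and after study drug, so Visit 7 ECGs cannot be assumed to precede dapagliflozin.
- A reader might infer that adverse events are double counted. SAP 4.10.2 places each event in the one period in which it began, which rules that out. The rule still needs the missing boundary to decide which period that is.
- A reader might infer that combination safety is visible nowhere else. Haematology and chemistry values are also summarised by time point, so Weeks 16 and 20 appear separately from Week 12.
- The D72 window matters only if the flag follows analysis visits, and nothing in the SAP links the two.
- All four arms follow the same rule, and no bias in the AZD5718-placebo comparison has been shown.
- SAP 4.12.1 records that the study stopped for lack of efficacy, with no safety concerns.

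**Conclusion.** The point holds for the treatment-emergent laboratory summary in SAP 4.10.4. Followed literally, the definitions place Visit 7 changes in the Period 2 summary although they arose without study dapagliflozin, and allow them in the Period 1 summary as well. Double counting follows from the wording; the SAP does not state it as an intention.

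The conclusion rests on one inference, that Visit 7 laboratory samples are drawn before the dose. The relative overstatement cannot be computed from the documents, and the illustrative range of 0 to 30-33% (46-49% without Follow-up) depends on the assumed rate and on equal, independent draws. A reader might take it that Period 2 incidence is inflated by about half. That needs near-complete independence within a participant and exclusion of the Follow-up draw, and the documents establish neither.

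Severity is minor to moderate: the tables are descriptive and no efficacy result changes.

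**What to change.** In SAP 4.5.1:
- Define the Week 12 flag as data collected after the first dapagliflozin dose, by date, and by time where recorded.
- For participants who enter Period 2, end the Monotherapy period immediately before that dose.
- Assign Visit 7 laboratory samples taken before the dose to Period 1 only.
- In SAP 4.10.2, use the same boundary to decide the period in which an adverse event starts.

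The cost is one definition and one derivation before the tables are run. The data are already collected: in-clinic dose date, and time if applicable (Protocol 6.4); laboratory collection date and time (SAP 3.2.2.3); and adverse event start date and time (Protocol 8.3.2). No vital-sign or ECG output needs to change on this account.
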